4 INTRODUCTION

The number of women diagnosed with breast cancer is increasing all over the world but little is done to lower these figures. The primary preventive measures that are available ranges from increased physical activity to prophylactic mastectomy. Several randomised controlled trials have shown a 40-60% decreased risk of breast cancer after anti-hormonal therapy (e.g. tamoxifen, raloxifen, aromatase inhibitors; [1]). Tamoxifen and aromatase inhibitors are normally used to treat breast cancer patients to reduce the risk of recurrence of the disease.

Despite the remarkable risk reduction in preventive randomised controlled trials, primary preventive strategies are scarcely part of clinical routine [1]. There are several possible reasons

for the reluctance, the major one being that the side effects of these therapies are not trivial. Serious side effects could only be acceptable for those that benefit from therapy, that is, there is a need of identifying women at high risk. Also, there is not a consensus on dose needed in the preventive setting. So far only full therapeutic dose has been tested and no attempts have been made to determine if lower doses prevent women from being diagnosed with breast cancer.

Karisma is an investigator-initiated study of primary prevention of breast cancer incidence. Karisma will be performed in three steps:

Karisma I, Pilot study

A previous application to Läkemedelsverket regarding the Karisma I study was accepted and the first pilot phase of Karisma was initiated in March 2015 and ended nine months later.

The exploratory pilot study including 42 women who were randomised to either 10 or 20 mg of tamoxifen. The aims of the pilot study were to identify the *time to mammographic density* change, difference of density change between 10 mg and 20 mg tamoxifen and piloting procedures.

The results from the pilot study show that density decreases within 6 months by about 50% for one quarter of the participants, about 20% for another quarter, and does not change for the remaining half of the participants.

As expected, there were more reported side effects in those groups with most density decrease. We noted no difference in the density reduction nor side effect spectra when we compared 10 and 20 mg tamoxifen. Approximately 25% of participants discontinued treatment due to adverse events and there was no dose dependant difference in discontinuation.

Karisma II (which this application refers to)

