7.1.3 Baseline (Month 0)

Meeting with Investigator

- The investigator will explain the nature and aim of the study, its procedures, possible side effects, requirements and restrictions.
- The woman will sign the ICF before any further study related procedures are performed.
- A woman fulfilling the inclusion and exclusion criteria will be randomised to one of the six treatment arms; tamoxifen 20 mg, 10 mg, 5 mg, 2.5 mg, 1 mg or placebo. All treatments will be on a daily basis for 6 months
- The woman will receive a sufficient amount of IMP in order to take one tablet daily during 6 months
- Screening form, randomization number and other applicable information will be filled in by investigator in the eCRF.
- The participants will be asked if they allow to have two biopsies of the normal breast tissue taken at month 0 and 6. This is optional and complies with a separate study protocol (Protocol: Biopsy Karisma II)

Procedures at baseline

After meeting with investigator when ICF is signed and randomization is performed, the following will be obtained:

- In total 24 ml blood will be collected. The blood will be analysed for tamoxifen metabolites, plasma hormones, plasma proteins, metabolic markers. In addition, DNA will be extracted and plasma aliquots will be biobanked for later analyses.
- The participants will be asked to fill out two web-based questionnaires;
 - The Karma questionnaire including lifestyle factors that influence risk of breast cancer such as age at first birth, breast-feeding, etc., demographic, medical history, quality-of-life, and concomitant medication.
 - o Karisma II baseline questionnaire including general symptoms and tamoxifen related symptoms
- Pregnancy test (urine) will be offered women of childbearing age for safety
- Measurement of weight, length and waist
- Instructions are given on how to use and report events by the Karma-app
- Biopsy of the breast. This is optional and complies with an additional translational study protocol (Protocol: Biopsy Karisma II)

7.1.4 1 month after baseline (+2/-1 weeks)

• Karisma II follow up questionnaire including general symptoms, tamoxifen related symptoms, compliance and health care contact connected to possible side effects

- 7.1.5 3 months after baseline (+/- 2 weeks)
 - Karisma II follow up questionnaire including general symptoms, tamoxifen related symptoms, compliance and health care contact connected to possible side effects

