## 6.9 Handling of missing data

The primary analysis will be performed on an ITT basis using the last-observation-carried-forward method. This analysis makes sense from an effectiveness (*de facto*) point of view, however it will likely bias the results towards equivalence for the primary efficacy endpoint (assuming that non-compliance is dose dependant) from an efficacy (*de jure*) point of view (i.e. compared to if no women dropped out from the study). We will therefore perform sensitivity analyses (Section 6.5) where we impute mammographic density 6 months into the study for women who dropped out. Specifically, we will use a multiple imputation protocol where mammographic density at 6 months is imputed using a regression model with density at the time points recorded within the study, age, HRT status, CYP2D6 polymorphisms, and endoxifen levels (at the available time points). The exact choice of multiple imputation model will be done using the study data after database lock using

cross-validation. We will also perform tipping point analyses with respect to the missing data by exploring how extreme the imputation of the missing data will need to be to change the overall conclusion of the trial (see also Section 6.5.1).

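### The imputation check in SAP 6.9 lists neither early symptom scores nor treatment arm, so under the SAP's own dose-dependent drop-out assumption it is likely to lean toward non-inferiority

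*SAP*

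**What the plan says.** SAP 6.9 carries the last observation forward in the primary analysis. It concedes that this probably pulls the result toward equivalence, "assuming that non-compliance is dose dependant", and offers multiple imputation as a sensitivity analysis (also SAP 6.5.1, item 4). In that analysis "mammographic density at 6 months is imputed using a regression model with density at the time points recorded within the study"; the full list of named predictors is "density at the time points recorded within the study, age, HRT status, CYP2D6 polymorphisms, and endoxifen levels (at the available time points". The model is not final: "The exact choice of multiple imputation model will be done using the study data after database lock using" cross-validation. A tipping-point analysis of the missing data is also planned.

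The protocol collects symptoms early. At months 1 and 3 (7.1.4 and 7.1.5) every woman is sent the "Karisma II follow up questionnaire including general symptoms, tamoxifen related symptoms, compliance and health care contact connected to possible side effects".

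On the pilot, Protocol section 4 reports that "there were more reported side effects in those groups with most density decrease", and also: "Approximately 25% of participants discontinued treatment due to adverse events and there was no dose dependant difference in discontinuation".

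SAP 6.6 plans for 30% drop-out and considers a fall to 10% or 15% in a lower-dose arm.

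**The concern.** A variable that predicts both the missing value and the fact that it is missing is the standard candidate for an imputation model. The pilot points to symptoms as such a variable: they went with larger density decrease, and adverse events were a reason for stopping. Without them, a woman who stops is imputed as if she were an ordinary completer with the same age, genotype and baseline density. If those who stop are more often strong responders, their decrease is understated, and more so in the arm that loses more women.

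Treatment arm is not listed either. If the regression is fitted across arms, imputed values are drawn toward a common mean and real differences between doses shrink.

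Imputation is offered as a counterweight to a primary analysis that the SAP itself expects to lean toward equivalence. If the check leans the same way, agreement between the two says less than it seems to.

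**Working it through.** **1. The plan's own figure.** The SAP 6.6 formula with one-sided alpha 0.015, 80% power, 50% responders in both arms and margin 16.7 gives (2.170 + 0.842)² × (50×50 + 50×50) / 16.7² = 9.07 × 5000 / 278.9 = 162.6, so 163 per arm. The SAP states 168, which is within 3%; power at 168 is 81.4%. Then 168/0.7 = 240. None of this is disputed.

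**2. What is known about a woman who stops and skips the exit visit.**

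| Predictor in SAP 6.9 | On-treatment value? |
|---|---|
| Density | No. Study mammograms fall at month 6 (and month 12 in Lund only) |
| Endoxifen | No. Blood is drawn at baseline and month 6 |
| Age, CYP2D6 | Fixed characteristics |
| HRT status | Varies little; oral HRT is excluded (Protocol 7.9, 7.11.7) |
| Month-1 and month-3 symptoms | Yes, if she was still answering, but not listed |

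The exit mammogram and blood sample are requested but not mandatory (Protocol 7.2).

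**3. How the lean arises.** The threshold is the median decrease at 20 mg, so about half of that arm respond by construction. If decreases at 20 mg are imputed too low, the threshold falls and women on the lower dose clear it more easily.

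**4. Simulation.** There were 400,000 women per arm. Density decrease Y is normal. Symptom score S = ρY + √(1−ρ²)·e, with e standard normal. Drop-out probability is Φ(c + γS), with c set to give the stated drop-out. The documents give neither ρ nor γ; the assumed ranges are ρ 0.2 to 0.5 and γ 0.5 to 1.0. Imputation is by arm, and the threshold is the completed-data 20 mg median. The listed covariates get no credit. Drop-out at 20 mg is 30% in the first three rows. Bias is in percentage points; positive means toward non-inferiority.

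| Lower-dose drop-out | No symptoms, true responders 33.3% (at the margin) | No symptoms, truly equal | With symptoms |
|---|---|---|---|
| 10% | +1.0 to +3.6 | +1.0 to +4.7 | within 0.3 of zero |
| 15% | +0.8 to +2.6 | +0.7 to +3.0 | within 0.3 of zero |
| 30% | −0.5 to +0.1 | −0.3 to +0.1 | within 0.3 of zero |
| 30-40%, against 25% at 20 mg (ρ 0.3, γ 1.0) | −0.6 to −2.0 | not run | within 0.1 of zero |

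**5. A second data model.** Responders are N(35, 15) and non-responders N(0, 8). Symptoms are 0.5 to 1.5 SD higher in responders, and drop-out log-odds rise 0.5 to 1.5 per SD (all assumed). Bias without symptoms is about +1 to +7 points at 30% versus 10-15% drop-out and +0.4 to +1.9 at equal drop-out. With symptoms it is about zero.

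**6. Arm also omitted.** In the model of step 4, imputing from the two arms pooled, without symptoms, gives +4.2 to +6.3 points at the margin, including +4.5 to +4.9 when drop-out is equal. If the arms are truly equal and drop-out is equal, it is −0.2 to +0.2. Only two arms were pooled here, whereas the trial has six.

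**7. Scale.** At the margin with 168 per arm, SE = √[(0.5×0.5 + 0.333×0.667)/168] = 5.3 points. The chance that a dose exactly at the margin passes the imputed check is 1 − Φ(2.170 − bias/SE). That is 1.5% with no bias, and 2.4%, 3.7% and 6.8% with a bias of 1, 2 and 3.6 points. This ignores between-imputation variance.

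**The case against.** **The pilot saw no dose difference in stopping.** This stands as a limit on direction. The pilot is the source for the symptom links, and it does not support unequal drop-out. It had 42 women on 10 or 20 mg only, and Protocol 7.5 calls its numbers too small for conclusions on side effects. The present trial adds 1, 2.5 and 5 mg and placebo in the belief that side effects will be fewer, and the SAP assumes dose dependence. So the direction is conditional on the SAP's premise.

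**The model is still open and will be chosen by cross-validation.** Symptoms could yet be added. But cross-validation scores prediction only where month-6 density was observed, so it cannot be relied on to reveal or repair selective loss.

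**Exit visits help.** A woman who attends brings an on-treatment density and endoxifen level into the listed model. The simulations ignore this, so their figures are nearer an upper bound for the assumed associations. Attendance is optional, and the time limit is 2 weeks after stopping, so the exit density need not be a month-6 value.

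**A tipping-point analysis is planned.** It probes departures from the imputation model and is a real safeguard. It does not correct the model, and SAP 6.9 does not tie it to symptoms or to the reason for stopping.

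**The sizes rest on assumptions.** This stands. The top of the second data model implies 46% drop-out among 20 mg responders against 14% among non-responders, which is strong. The protocol does not report density response among pilot women who stopped, nor does either document give the timing of drop-out. Protocol 7.6 places side effects typically in the first 3 months, so some women may stop before a month-3 or even a month-1 score exists.

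**Conclusion.** The point holds in conditional form. The listed predictors omit early symptom scores and treatment arm, although the symptom data are collected and the pilot gives reason to use them. Under the SAP's 30% versus 10-15% drop-out, the imputed check is likely to lean toward non-inferiority. The lean is about 1 to 5 points against a 16.7-point margin, with assumed associations, imputation by arm and no credit for the listed covariates. A different data model reaches about 7 points at its extreme.

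A reader might infer two stronger things. One is that the check is biased toward non-inferiority whatever happens. The documents do not support that: the lean is near zero with equal drop-out (under 2 points in the second model) and can reverse if lower doses lose more women. The other is that the trial's false-positive rate is inflated by the amounts in step 7. Those figures apply to the imputed check alone; the primary analysis uses a different method.

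The case for the change does not depend on the direction. In every scenario run, including the reversed ones, adding symptoms within arm brought the bias close to zero.

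**What to change.** Before database lock, state in SAP 6.9 that:

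- imputation is done within arm, or with arm as a predictor;
- the available month-1 and month-3 FACT-ES and general-symptom scores enter as auxiliary variables, using the last score before stopping;
- stopping for an adverse event and time on treatment define scenarios in the planned tipping-point analysis. They should not be within-arm regression terms, because women who complete treatment hardly vary on them and the coefficients could not be learned.

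The cost is SAP wording and a slightly larger imputation model; no new data are needed. One limit remains: a woman who stops before month 1 has only a baseline score, so for her the tipping-point scenarios must carry the weight.
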